## 7.3 Surgical Procedure

The surgical procedure will be performed using intraocular microsurgical techniques and anesthesia per the investigator's standard procedure. The CyPass Micro-Stent will be implanted according to the Instructions for Use (IFU) for CyPass System 231.

Topical antibiotics and anti-inflammatory medication, as well as Apraclonidine, Brimonidine or other topical hypotensive agents may be administered at the conclusion of the procedure. The topical antibiotic/steroid/NSAID medication regimen described in Table 8 below is recommended during the initial postoperative month.

Medication Regimen								
Time Period	Antibiotic	Steroid	NSAID					
Surgery Day – Week 1	4 th generation fluoroquinolone (e.g., moxifloxacin) QID	e.g., prednisolone acetate 1% QID	e.g., ketorolac QID					
Week 2	N/A	e.g., prednisolone acetate 1% TID	e.g., ketorolac QID					
Week 3	N/A	e.g., prednisolone acetate 1% BID	e.g., ketorolac QID					
Week 4	N/A	e.g., prednisolone acetate 1% QD	N/A					

## Table 8

Adjustments in the duration of postoperative medications may be necessary for subject safety.

# 7.4 Ocular Hypotensive Medication Re-Introduction

# 7.4.1 Medication Re-Introduction During 1st Postoperative Month

Ocular hypotensive therapy may be initiated within the first postoperative week if the subject's IOP > 21 mmHg. Additional IOP-lowering medication can be used with investigator discretion as necessary for IOP control.

## 7.4.2 Medication Re-Introduction After 1st Postoperative Month

Topical IOP lowering therapy may be initiated if the subject's IOP > 21 mmHg. Only 1 medication should be added at a visit. The preferred order of medication reintroduction should be as follows:

- Prostaglandin analogues
- Beta blockers
- Carbonic Anhydrase inhibitors
- Alpha agonists

Adjustments in IOP lowering therapy may be necessary for subject safety and should be based on investigator discretion.

# 7.5 Study Visits

Study subjects will participate in follow-up visits through 12 months postoperatively in accordance with Appendix 1 -Study Examinations and Procedures.

#### 7.5.1 Unscheduled Visits

An unscheduled visit is any visit to the clinical site (other than those specified in the protocol), during which the subject has a complaint regarding the study eye or study eye treatment is required. No specific testing is required at unscheduled visits.

# 7.6 Subject Disposition

#### 7.6.1 Terminated Subjects

Subjects may be terminated (exited) from the study early due to:

- Screen failure
- AE(s)
- Administrative reasons (e.g., voluntary withdrawal, lost to follow-up)

Subjects who are terminated prior to surgery will not be followed beyond the date of termination unless the reason for termination in an IOP-related adverse event (AE). These subjects will be followed until resolution or stabilization of the AE. Subjects who are terminated prior to surgery due to a non-IOP-related AE will not be followed beyond the date of the AE report. Subjects who undergo surgery but do not receive the CyPass due to a surgical AE will be followed until resolution or stabilization of the AE. Subjects who receive the CyPass Micro-Stent but are terminated from the study should be followed for safety until the end of study period.

Study sites must make every attempt to follow-up on subjects who do not return for scheduled study examinations. If a subject is non-responsive to these follow-up attempts, he/she will be considered to be lost to follow-up. The sponsor should be notified promptly regarding subjects who are terminated prior to study completion.

Subjects terminated after implantation of the CyPass Micro-Stent will not be replaced.

## 7.6.2 Completed Subjects

Completed subjects are those subjects who have not been terminated from the study prior to their completion of follow up.

## 8. STATISTICAL METHODS

#### 8.1 Sample Size

The primary effectiveness endpoint is the outcome of  $\geq 20\%$  decrease in IOP from baseline without IOP lowering medications up to 12 months post-operatively (IOP response). The proportion of eyes meeting the effectiveness outcome, IOP response rate, will be assessed at 12 months. A sample of at least 101 eyes will be enrolled across the two groups (CyPass only control and CyPass + Healon 5 dose selected) with an estimated 86 eyes completing their month 12 visit. Assuming a 30% success rate for the control eyes and a 60% success rate for the visco-assisted eyes, 80% power can be achieved with 43 eyes per arm using a two-tailed alpha of 0.05.

## 8.3 Efficacy and Safety Analyses

The primary effectiveness endpoint, the achievement of a 20% decrease in IOP relative to baseline in the absence of IOP lowering medications will be summarized at each postoperative visit by the number available for analysis (N), the proportion meeting success criteria, and the 95% confidence interval (CI).

Secondary endpoints describing proportions meeting given criteria will be summarized at each postoperative visit by N, percentage and 95% CI. Continuous endpoints, IOP, mmHg decrease

in IOP and % decrease in IOP will be summarized by N, mean, standard deviation median, minimum and maximum. For continuous change measures, the 95% CI of that change will also be provided.

The safety profile of the CyPass device will be based on intraoperative and postoperative adverse event rates, slit lamp biomicroscopy and fundus examination. All subjects who undergo CyPass implantation surgery will be included in the safety analysis. The incidence of adverse events will be summarized by N, percentage, and CI.

An adverse event (AE) is any untoward medical occurrence, unintended disease or injury or any untoward clinical sign occurring in a study subject, whether or not related to the CyPass Micro-Stent. All AEs in the study eye must be reported on the appropriate CRF. Each AE must be graded by degree of harm to the subject (note grading scale below), as well as by the relationship to study device or implantation procedure.

AEs should be graded as follows:

- Mild: Discomfort noticed but no disruption of normal daily activity
- Moderate: Discomfort sufficient to reduce or affect normal daily activity
- Severe: Incapacitating with inability to work or perform normal daily activity

Ocular conditions or diseases that are chronic but stable and do not render the subject ineligible for the study should be recorded under the subject's ocular history. Changes in the chronic condition or disease consistent with natural progression are not considered AEs.

AEs associated with glaucoma surgical procedures that might reasonably be expected to occur in this study are listed below. These anticipated AEs include, but are not limited to:

# 9.1 Intraoperative Adverse Events

- Lens touch
- Choroidal detachment
- Inadvertent perforation of sclera
- Hyphema, which obscures surgeon's view
- Inadvertent loss of vitreous
- Choroidal hemorrhage or effusion
- Significant iris injury or trauma
- Significant corneal damage
- Zonular dialysis

# 9.2 Postoperative Adverse Events

- Chronic pain in the study eye present at 3 months postoperatively or later
- Flat anterior chamber with lens/cornea touch
- Shallow chamber with peripheral iridocorneal apposition
- BCVA loss of 3 Snellen lines compared to baseline at 3 months postoperatively or later
- Hypotony (defined as IOP < 6 mmHg) at 1 month postoperatively or later
- Maculopathy
- Hypotonic maculopathy
- CyPass obstruction causing an untoward effect in the study eye
- CyPass malposition
- CyPass migration, causing an untoward effect in the study eye
- Wound dehiscence
- Persistent anterior chamber cell and flare requiring steroid treatment after 2 months postoperatively
- Endophthalmitis
- Cataract formation or progression outside of expected progression
- Persistent hyphema present at 1 week postoperatively or later
- Corneal opacification, or corneal decompensation
- Significant corneal edema
- Retinal complications (dialysis, flap tears, retinal detachment, or proliferative vitreoretinopathy)

- Choroidal hemorrhage or choroidal effusion, defined as a choroidal effusion or detachment with at least a partially hemorrhagic component that obstructs vision or causes pain (including both peripheral and "kissing" choroidal detachments) lasting longer than 1 month
- Significant elevation in IOP requiring non-medical intervention
- Other events resulting in unplanned ocular surgical reintervention (other than paracentesis to relieve pressure prior to 1 week postoperative or Nd:YAG laser procedure for treatment of posterior capsular opacification)
- Loss of eye
- Significant ptosis
- Atrophy/phthisis
- Significant foreign body sensation at or after 3 months postoperative
- Increase in C:D ratio of  $\geq 0.3$  units on slit lamp biomicroscopic examination
- Confirmed increase in visual field loss outside of expected progression

## 9.3 Serious Adverse Events

An AE should be classified as serious, regardless of relationship to the CyPass Micro-Stent if it:

- Led to death
- Led to a serious deterioration in health that:
  - Resulted in a life-threatening illness or injury, or
  - Resulted in a permanent impairment of a body structure or a body function, or
  - Required in-patient hospitalization or prolongation of existing hospitalization, or
  - Resulted in medical or surgical intervention to prevent life-threatening illness or injury or permanent impairment to a body structure or a body function
- Led to fetal distress, fetal death or a congenital abnormality or birth defect

# Serious Adverse Events (SAE) must be reported to Transcend Medical within 1 week of learning of the event.

## 9.4 Serious Adverse Device Effects

A serious adverse device effect (SADE) is an adverse event related to the use of the CyPass Micro- Stent that resulted in any of the consequences characteristic of a SAE. SADEs must be reported to **Transcend Medical within 24 hours of learning of the event.** 

#### 9.5 Device Deficiencies

A device deficiency is considered to be an inadequacy of the CyPass Micro-Stent System that is related to its identity, quality, durability, reliability, safety or performance (e.g., malfunction, misuse or user error, inadequate labeling). Device deficiencies must be reported to Transcend Medical within 1 week of learning of the deficiency.

To report any SAE, SADE or device deficiency, please contact:

## **10. STUDY MONITORING PLAN**

On-site monitoring visits will be performed periodically to assess the progress of the study and identify concerns related to adherence to the study protocol, EC review of the study and maintenance of study-related records and reports. Remote monitoring will be conducted and subject eligibility will be approved by the Sponsor prior to randomization.a.

# 11. DATA MANAGEMENT PLAN

Clinical study data will be documented on study-specific Case Report Forms (CRFs) and maintained in an electronic database, which has been established and validated for study use. The Sponsor will confirm data entry accuracy and issue data queries as necessary. Clinical study data will be maintained for the duration of the study until completion of the final clinical study report. Thereafter, the data will be archived by Sponsor.

# 12. ETHICAL AND REGULATORY CONSIDERATIONS

This protocol was designed and will be conducted, recorded, and reported in compliance with the principles of Good Clinical Practice (GCP). These requirements are stated in global regulations as well as "Guidance for Good Clinical Practice", International Conference on Harmonization (ICH). The study will be performed in accordance with the recommendations guiding physicians in biomedical research involving human subjects adopted by the 18th World Medical Assembly, Helsinki, Finland, 1964 and later amendments.

#### 12.1 Sponsor Responsibilities

The Sponsor is responsible for the following activities with respect to this clinical investigation:

- Clinical quality assurance and quality control
- Clinical investigation planning and conduct, including: Selection of clinical personnel, Preparation of clinical investigation documents and materials, Clinical investigation conduct, Clinical investigation monitoring, Safety evaluation and reporting and Clinical investigation close-out

The Sponsor will maintain clinical study records throughout the study and for at least two years from the date on which the study was terminated or completed, and for providing access to these records for audit and inspection by regulatory authorities.

Additionally, the Sponsor is responsible for providing reports on the study progress and performance in accordance with applicable regulatory requirements.

## 12.2 Investigator Responsibilities

The principal investigator at each site is responsible for implementation and management of the day-today conduct of the clinical investigation as well as to confirm data integrity and the rights, safety and well-being of the subjects involved in the clinical investigation.

The principal investigator must sign an Investigator Agreement acknowledging that he/she will comply with the protocol and other study obligations, including safety reporting. No changes in this protocol can be made without the Sponsor's written approval.

All Investigators must participate in a protocol review conducted by the Sponsor or the Sponsor's designated representative.

Investigators are responsible for maintaining clinical study records throughout the study and for at least two years from the date on which the study was terminated or completed, and for providing access to these records for audit and inspection by regulatory authorities.

## 12.3 Institutional Review

Before enrollment of any study subjects, the protocol and the subject ICF must be reviewed and approved by an EC that is operating in accordance with local procedures and regulatory requirements.

It is the responsibility of the Investigator to obtain and maintain approval for the study protocol and ICF, and to keep the EC informed of the occurrence of serious adverse events. It is also the Investigator's responsibility to maintain a file of all correspondence with the EC and to forward copies of that correspondence to the Sponsor or Sponsor's designated representative.

## 12.4 Subject Informed Consent and Confidentiality

Written informed consent is required prior to initiation of study-specific procedures or exams on study subjects. It is the responsibility of the Investigator to complete the informed consent process and to provide each subject with a copy of the fully executed ICF. The principal investigator and Sponsor (or designee) will use every effort will to ensure that subject names or other personal identifiers are not be used during the course of the study. All subject data will be kept in a secure location.

#### 12.5 Device Accountability

Study devices will be shipped to the site or hand carried to the site by the Sponsor or Sponsor's designee. Study device shipment records should be verified by comparing the shipping receipt confirmation to devices received at the site. Study devices should be stored in a secure area to prevent unauthorized distribution.

The Investigator will be responsible for keeping current and accurate records of devices dispensed and implanted. After completion of study enrollment, all non-used study devices will be returned to the Sponsor or Sponsor's representative.

## **13. PUBLICATION POLICY**

All publications and/or presentations concerning this study must be reviewed by the Sponsor prior to publication/presentation.

6.3.9	Secondary Surgical Interventions	22
6.3.10	CyPass Explantation and/or Repositioning	
6.3.11	Device Deficiencies	
7	Sample Size and Power Calculations	
		23

Document: TDOC-0053376 Version: 2.0; Most-Recent; Effective; CURRENT

Status: Effective

List of Abbreviations

ADE	Adverse device effect
AE	Adverse event
BCVA	Best corrected visual acuity
CER	Clinical evaluation report
CI	Confidence interval
CSR	Clinical study report
FAS	Full analysis set
ICF	Informed consent form
IOP	Intraocular pressure (mmHg)
ITT	Intent-to-treat
OAG	Open angle glaucoma
OD	Right eye
OS	Left eye
OU	Both eyes
SADE	Serious adverse device effect
SAE	Serious adverse event
SAS®	Statistical analysis system
SD	Standard deviation
TEAE	Treatment emergent adverse event

Document: TDOC-0053376 Version: 2.0; Most-Recent; Effective; CURRENT

Status: Effective

1 Study Objectives and Design

1.1 Study Objectives

The purpose of this research study is to assess the safety and effectiveness of visco-assisted CyPass Micro-Stent implantation for the lowering of intraocular pressure (IOP) in patients with open angle glaucoma (OAG).

1.2 Study Description

This is a prospective, randomized, controlled, multicenter, interventional study performed in two phases, as stated below. Up to 150 eyes meeting subject eligibility criteria listed in Section 6 of the protocol will be randomized to study treatment at up to 10 investigational sites.

Note, only one eye per subject may be treated under the study protocol. If both eyes qualify for the study, the study investigator will choose which eye will be the study eye. Unless specified otherwise, ocular results refer to the study eye only. Therefore, throughout this SAP and corresponding tables and data listings, the number of subjects and eyes are synonymous.

Dose Selection Phase: During this phase, the first cohort (Cohort 1) of 63 subjects was randomized (1:1:1) to receive either a CyPass Micro-Stent with 30 μl adjunct Healon 5 viscoelastic, a CyPass Micro-Stent with 60 μl of adjunct Healon 5 viscoelastic, or a CyPass Micro-Stent without adjunct viscoelastic. After completion of at least 3 months follow-up on all subjects in this phase, an interim review of safety and efficacy data was performed to determine the optimum dose of adjunct viscoelastic for the study expansion phase.

Expansion Phase: After the dose selection phase, the study was expanded to include a second cohort (Cohort 2) of up to 90 additional subjects who were randomized 1:1 to either the CyPass Micro-Stent without adjunct viscoelastic or to the CyPass Micro-Stent with 60 μ l adjunct viscoelastic (the dose selected based on Dose Selection Phase results).

Visit Schedule and Visit Windows: Enrolled study subjects are expected to participate in the study from Screening/Baseline through 12 months postoperatively in accordance with Table 1 – Study Examinations and Procedures (Appendix 1 in the study protocol) below.

Note, prior to protocol version D, Amendment dated 07Oct2014, the 12 Month Washout visit was not required for mainly the initial dose selection phase subjects who were on IOP lowering medication. All Cohort 2 patients were enrolled under protocol version D or a later version.

Version: 2.0; Most-Recent; Effective; CURRENT

Status: Effective

Document: TDOC-0053376 Version: 2.0; Most-Recent; Effective; CURRENT

Status: Effective

1.3 Randomization

Subjects were randomized to their assigned treatment on the day of their surgical procedure. Randomization lists were provided for each study site.

During the Dose Selection Phase of the study, subjects were randomized in Cohort 1 using a 1:1:1 schedule to receive either CyPass Micro-Stent with 30 μ l of adjunct Healon viscoelastic, CyPass Micro-Stent with 60 μ l of adjunct Healon viscoelastic, or the CyPass Micro-Stent with no adjunct Healon viscoelastic.

During the Expansion Phase of the study, subjects were randomized in Cohort 2 using a 1:1 schedule to receive either CyPass Micro-Stent without adjunct Healon viscoelastic or the CyPass Micro-Stent with 60 µl of adjunct Healon 5 viscoelastic.

1.4 Masking

This study was not masked. Treatment assignment may be known to the investigators, subjects, or Alcon personnel involved with the planning and execution of the study.

Document: TDOC-0053376 Version: 2.0; Most-Recent; Effective; CURRENT

Status: Effective

2 Analysis Sets

All subjects will be considered enrolled once they have signed the informed consent form.

2.1 Full Analysis Set

The full analysis set (FAS) will serve as the primary set for the efficacy analyses. The FAS includes all randomized subjects who undergo CyPass implantation surgery.

All primary and secondary endpoint summaries will be carried out using the FAS analysis set; that is, subjects assigned to the treatment to which they were randomized.

2.2 Safety Analysis Set

Safety analyses will be conducted using the safety analysis set on a treatment-emergent basis. The safety analysis set will include all enrolled subjects who undergo CyPass implantation surgery. For treatment-emergent safety analyses, subjects/eyes will be categorized under the actual treatment received. Therefore, subjects/eyes exposed to an incorrect study treatment will be included in the group corresponding to the actual treatment received. All listings of safety data will use the Safety Set.

3 Statistical Methods

Statistical analyses will be performed to summarize the primary and secondary efficacy endpoints as well as key safety evaluations. Additionally, within each treatment, changes from baseline will be assessed where appropriate.

3.1 General Reporting Conventions

- Only one eye per subject may be treated under the study protocol. If both eyes qualify
 for the study, the study investigator will choose which eye will be the study eye.
 Unless specified otherwise, all ocular results refer to the study eye only. Therefore,
 throughout this SAP and corresponding tables and data listings, the number of
 subjects and eyes are synonymous.
- Available data at each assessment time point will be presented. No imputations will be made for missing data.

Document: TDOC-0053376 Version: 2.0; Most-Recent; Effective; CURRENT

Status: Effective

- Appropriate descriptive statistics will be computed and displayed by assessment time point for both continuous and categorical variables. For continuous variables, descriptive statistics include n (number of subjects/eyes) with non-missing data, mean, standard deviation (SD), median, minimum and maximum values. For categorical parameters, the number and percentage of subjects/eyes within each category will be presented. The denominator for percentages will be based on the number of subjects with non-missing data appropriate for summary purposes. Unless otherwise noted, percentages will be presented to one decimal place. Any confidence intervals (CI) will be at the alpha = 0.05 (two-sided) level.
- Summary tables will be presented by treatment and overall, as appropriate, for both phases/cohorts combined.
- Study day: Study day will be calculated relative to the date of stent implantation surgery (Day 0) as: Date of event – date of surgery. This formula will be used when calculating days to a specific event (i.e., ocular medications and/or AE start date). A negative study day indicates an event prior to surgery.
- Individual data listings of select data represented on the eCRF will be provided to facilitate investigation of the tabulated values and to allow for clinical review of key variables. All data listings will be sorted by Treatment (i.e., CyPass, CyPass with 30 μl, and CyPass with 60 μl), Cohort (1 or 2), site-subject number, visit, and assessment time points where appropriate. Data from unscheduled visits will be excluded from the summary tables (except for adverse events) but included, chronologically, in the data listings.
- Analyses will be generated using SAS® version 9.2 or higher.

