## 4.2.3 ViscoPass Study (Initial Phase)

During the Dose Selection Phase of this study, 62 subjects were randomized using a 1:1:1 schedule to receive either CyPass Micro-Stent with 30 µl of adjunct Healon viscoelastic, CyPass Micro-Stent with 60 µl of adjunct Healon viscoelastic, or the CyPass Micro-Stent with no adjunct Healon viscoelastic.

With 6 months follow-up on all subjects, there was no difference in safety among the three arms, and the 60  $\mu$ l arm had a comparable rate of AEs to either the Cypass only arm or the 30  $\mu$ l arm. Also, there were no unanticipated or vision-threatening adverse events in either group. Additionally, there was a trend towards higher efficacy with the 60  $\mu$ l arm compared to the other two arms for the primary and secondary efficacy outcomes.

Based on the results of the initial phase and considering the risk-benefit profile of each arm, the 60  $\mu$ l arm was selected as the go-forward dose with recommended discontinuation of the 30  $\mu$ l arm which had no appreciable benefit in either safety or efficacy.

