5.3 Statistical Methods for Efficacy Analyses

The primary efficacy endpoint, the achievement of a 20% decrease in IOP relative to baseline in the absence of IOP lowering medications up to 12 months post-operatively will be summarized at each post-operative visit by the number and percent of subjects having IOP response and the corresponding 95% confidence interval (CI) based on the exact binomial distribution.

[figure not shown]
Secondary efficacy endpoints describing proportions meeting given criteria will be summarized at each post-operative visit by the number and percentage of responses and the corresponding 95% CI based on the exact binomial distribution. While descriptive statistics for all continuous parameters for the actual values and change from baseline, including the 95% CI of the actual/observed results (based on a *t*-distribution) and change (based on a paired *t*-distribution), will be provided for each protocol specified visit, the 12 month visit is of most interest.

All efficacy analysis summaries will be produced using the FAS set.

Document: TDOC-0053376 Version: 2.0; Most-Recent; Effective; CURRENT

Status: Effective

Document: TDOC-0053376 Version: 2.0; Most-Recent; Effective; CURRENT

Status: Effective

6 Safety Analysis Strategy

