6.3.4 Intraocular Pressure

Intraocular pressure (IOP) measurements will be recorded in mmHg and reported up to one decimal place. IOP measurements will be summarized relative to both medicated and unmedicated baseline assessments compared to postoperative visits as follows. For medicated baseline IOP, descriptive summaries of observed values, as well as change and percent change from medicated baseline (Baseline1) values will be presented at each postoperative assessment visit compared to medicated baseline. Similarly, descriptive

Document: TDOC-0053376 Version: 2.0; Most-Recent; Effective; CURRENT

Status: Effective

summaries of observed values, as well as change and percent change from unmedicated baseline (Baseline2) values will be presented at each postoperative assessment visit compared to unmedicated baseline.

Further, IOP measurements over time at the Screening, Baseline, 1 Mo, 3 Mos, 6 Mos, 12 Mos, and 12 Mos unmedicated assessments will be presented graphically using side-by-side box plots to compare results between the CyPass alone and CyPass with 60 µL groups.

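### SAP 3.1 pools the eyes used to choose 60 µl with those randomised afterwards, and no visible summary shows Cohort 2 alone; the pooled 60 µl response rate carries a small upward selection bias (about 0 to 2.5 points under stated assumptions)

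*SAP*

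**What the plan says.** **How the dose was chosen.** SAP 1.2 records that after at least 3 months of follow-up in Cohort 1, "an interim review of safety and efficacy data was performed to determine the optimum dose of adjunct viscoelastic for the study expansion phase". Protocol 4.2.3 reports, with 6 months of follow-up, a tendency to better efficacy at 60 µl "compared to the other two arms for the primary and secondary efficacy outcomes". The choice was made "Based on the results of the initial phase and considering the risk-benefit profile of each arm", so safety was weighed as well.

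**How results are presented.** SAP 3.1 sets the reporting rule: "Summary tables will be presented by treatment and overall, as appropriate, for both phases/cohorts combined". SAP 2.1 adds: "All primary and secondary endpoint summaries will be carried out using the FAS analysis set". The FAS is not restricted by cohort.

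**What is estimated.** SAP 5.3 summarises the primary endpoint at each visit by "the number and percent of subjects having IOP response and the corresponding 95% confidence interval (CI) based on the exact binomial distribution". The visible text has no between-arm difference or test for it. SAP 6.3.4 plans "side-by-side box plots to compare results between the CyPass alone and CyPass with 60" µl.

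**Where cohort appears.** In the visible analysis text, cohort is only a sort key or a variable in listings. SAP 3.1 says: "All data listings will be sorted by Treatment", then by cohort.

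**A rule that changed between cohorts.** SAP 1.2 and 5.1 note that before protocol version D the Month 12 Washout visit was not required. This affected mainly dose-selection subjects on IOP-lowering medication. All Cohort 2 subjects enrolled under version D or later.

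**The concern.** When an arm is carried forward partly because its early results looked better, those results are on average higher than the arm's true rate. Pooling them with later data passes part of the excess into the final estimate. Here it would sit in the headline figure, the pooled 60 µl response rate and its interval, and in any contrast with control drawn from the tables or the box plots.

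Eyes randomised after the dose was fixed give an estimate free of this bias. In the visible SAP, a reader who wants it must rebuild it by hand from the cohort-sorted listings.

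**Working it through.** **The plan's own figure.** SAP 7 assumes 30% vs 60%, two-sided alpha 0.05 and the likelihood-ratio chi-square test, and gives 43 eyes per arm for 80% power. The noncentral chi-square calculation gives power 0.796 at 42 and 0.805 at 43, so 43 reproduces.

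**Inputs from the documents.**
- Cohort 1: 63 subjects at 1:1:1 (SAP 1.2), so 21 per arm. Protocol 4.2.3 gives 62, which makes no material difference.
- Cohort 2: up to 90 at 1:1 (SAP 1.2), so at most 45 per arm.
- Control plus selected dose: at least 101 eyes (SAP 7), which leaves (101 − 42)/2 = 29.5 per arm for Cohort 2.
- Cohort 1 share of those two arms: 42/101 = 42% at the minimum, and 42/(42 + 90) = 42/132 = 32% at the Cohort 2 cap.

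**Assumptions not in the documents.** The dose with more interim responders is chosen, with ties split at random. The interim-to-Month-12 correlation within an eye is 0.3 to 1.0. True rates are as listed below.

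**Closed form for equal doses.** The larger of two independent proportions, each with true rate p and n₁ eyes, exceeds p on average by about √[p(1 − p)/n₁]/√π. Pooling multiplies this by n₁/(n₁ + n₂), and imperfect correlation r multiplies it by r. With n₁ = 21 and r = 1:
- p = 0.45, n₂ = 30: √(0.2475/21) = 0.1086; divided by 1.772 = 0.0612; times 21/51 = 0.0252, or **2.5 points**.
- p = 0.30, n₂ = 45: √(0.21/21) = 0.1000; divided by 1.772 = 0.0564; times 21/66 = 0.0180, or **1.8 points**.

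**Simulation** (200,000 to 400,000 runs per cell), bias in points given that 60 µl was selected:

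| True rates, control/30 µl/60 µl | Cohort 2 per arm | r = 0.3 to 0.7 | r = 1.0 |
|---|---|---|---|
| 30/30/30 | 45 | 0.52 to 1.24 | 1.80 |
| 30/30/30 | 29 | 0.70 to 1.71 | 2.31 |
| 30/60/60 | 45 | 0.57 to 1.31 | 1.91 |
| 30/60/60 | 29 | 0.76 to 1.80 | 2.50 |
| 30/45/60 | 45 | 0.22 to 0.52 | 0.71 |
| 30/45/60 | 29 | 0.30 to 0.68 | 0.94 |
| 30/30/60 | 29 to 45 | about 0.0 to 0.14 | 0.2 |

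The closed form and the simulation agree for equal doses. When 60 µl is truly much better than 30 µl, it is selected almost regardless of chance and the bias is close to zero.

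**Where the bias sits.** Under this rule control plays no part in the choice, so the bias in the pooled control rate is about 0. The whole bias is in the pooled 60 µl rate and passes unchanged into 60 µl minus control. The Cohort 2 contrast alone is within 0.1 points of unbiased throughout.

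**Scale.** The 95% CI half-width for a difference at 30% vs 60% is 1.96 × √[(0.24 + 0.21)/n]. This gives 20.1 points at 43 per arm, 20.8 at 40 and 24.0 at 30.

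**The case against.** **The analysis may already exist.** The SAP contents list shows untitled entries after 5.1 and after 5.3, and SAP 3.1 is a general convention qualified by the words on appropriateness. A reader might infer that the SAP has no Cohort 2 analysis. The documents do not support that; they show only that none is visible. The SAP also rests on protocol Version F, while the protocol supplied is Version D. This objection stands, and the fix allows for it.

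**The bias is immaterial and pooling is the better estimator.** Both are largely true. The bias is small beside a 30-point difference with a half-width of about 20. The root mean squared error is about 8 points pooled against 10 for Cohort 2 alone at 45 per arm, and 9 against 12 at 30 per arm. Because safety was also weighed, the bias is probably below the top of the range. Pooling fits the sizing too, since Cohort 2 is capped at 90, below the 101 eyes planned. This rules out replacing the pooled result; it does not argue against a supportive table.

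**The facts are already disclosed.** SAP 1.2 says that Cohort 1 informed the dose, and SAP 3.1 says that tables are pooled. A reader of the tables alone may see neither, and rebuilding Cohort 2 from listings is laborious.

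**A by-cohort comparison is not a clean test of replication.** This stands. SAP 3.1 imputes nothing, and SAP 5.1 counts only eyes with non-missing IOP. With the earlier washout rule, ascertainment of unmedicated Month 12 IOP may differ between cohorts.

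**Stronger readings to avoid.** A reader might infer an inflated error rate, but no between-arm test is visible. A reader might infer that cohort confounds 60 µl vs control, but allocation between those arms is equal within each cohort. A reader might expect a larger bias because 60 µl also had to beat control, but Protocol 4.2.3 does not state that as a condition.

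**Conclusion.** The point holds as one of transparency with a small, directional bias. The pooled 60 µl response rate, its exact interval and any contrast with control are expected to be too high by about 0 to 2.5 points. The range rests on an assumed rule (more interim responders wins), 21 eyes per arm in Cohort 1, 30 to 45 in Cohort 2, and a correlation of 0.3 to 1.0. The top needs equal doses and a correlation of 1.0; the bottom applies when 60 µl is clearly better than 30 µl. Nothing here would by itself alter how a 30-point difference is read. What the visible plan lacks is a tabulated estimate from eyes randomised after the dose was fixed.

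**What to change.** 1. In SAP 3.1, keep the pooled summaries and footnote them as including the data used to select the dose.
2. In SAP 5.3, add one supportive table for Cohort 2 alone, covering the primary endpoint and the secondary efficacy endpoints, with the 60 µl minus control difference and its 95% CI.
3. Beside it, show the number of eyes per arm and cohort with an unmedicated Month 12 IOP. State that differences between cohorts should not be read as selection bias alone, because the washout requirement changed.
4. If a section not shown already does this, cross-refer to it from SAP 3.1.

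The cost is a few tables and no new data. The Cohort 2 estimate is less precise, with a half-width of about 21 to 24 points at 40 to 30 eyes per arm against about 20 at the planned 43. It should therefore accompany the pooled result and not replace it.
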